11.2 Neck disability index (NDI) (Vernon, 2008)

Originally published in 1991 in the Journal of Manipulative and Physiological Therapeutics, the Neck Disability Index (NDI) is an instrument to measure patient-reported disability secondary to neck pain. It was developed utilizing the Oswestry Low Back Pain Index as a model and therefore, at the time of its creation, was distinguished from other simpler pain assessments by examining patient function with respect to activities of daily living.

The instrument has 10 items and patients rate their pain from 0 (no pain) to 5 (worst imaginable pain). Individual item responses are summed to a total score, where 0 points indicate no activity limitations, and 50 points indicate complete activity limitation. This instrument may be useful in patients with chronic or acute onset neck pain and in patients with musculoskeletal complaints or with cervical radiculopathy.

1. Pain Intensity:

I have no pain at the moment +0

The pain is very mild at the moment +1

The pain is moderate at the moment +2

The pain is fairly severe at the moment +3

The pain is very severe at the moment +4

The pain is the worst imaginable at the moment +5

2. Personal Care (Washing, Dressing, etc.)

I can look after myself normally without causing extra pain +0

I can look after myself normally but it causes extra pain +1

It is painful to look after myself and I am slow and careful +2

I need some help but can manage most of my personal care +3

I need help every day in most aspects of self care +4

I do not get dressed, I wash with difficulty and stay in bed +5

3. Lifting

I can lift heavy weights without extra pain +0

can lift heavy weights but it gives extra pain +1

Pain prevents me lifting heavy weights off the floor, but I can manage if they are conveniently placed, for example on a table +2

Pain prevents me from lifting heavy weights but I can manage light to medium weights if they are conveniently positioned +3

I can only lift very light weights +4

I cannot lift or carry anything +5

4. Reading

I can read as much as I want to with no pain in my neck +0

I can read as much as I want to with slight pain in my neck +1

I can read as much as I want with moderate pain in my neck +2

I can't read as much as I want because of moderate pain in my neck +3

I can't hardly read at all because of severe pain in my neck +4

I cannot read at all +5

5. Headaches

I have no headaches at all +0

I have slight headaches, which come infrequently +1

I have moderate headaches, which come infrequently +2

I have moderate headaches, which come frequently +3

I have severe headaches, which come frequently +4

I have headaches almost all the time +5

6. Concentration

I can concentrate fully when I want to with no difficulty +0

I can concentrate fully when I want to with slight difficulty +1

I have a fair degree of difficulty in concentrating when I want to +2

I have a lot of difficulty in concentrating when I want to +3

I have a great deal of difficulty in concentrating when I want to +4

I cannot concentrate at all +5

7. Work

I can do as much work as I want to +0

I can only do my usual work, but no more +1

I can do most of my usual work, but no more +2

I can't do my usual work +3

I can hardly do any work at all +4

I can't do any work at all +5

8. Driving

I can drive my car without any neck pain +0

I can drive my car as long as I want with slight pain in my neck +1

I can drive my car as long as I want with moderate pain in my neck +2

I can't drive my car as long as I want because of moderate pain in my neck +3

I can hardly drive at all because of severe pain in my neck +4

I can't drive my car at all +5

9. Sleeping

I have no trouble sleeping +0

My sleep is slightly disturbed (less than 1 hr sleepless) +1

My sleep is mildly disturbed (1-2 hrs sleepless) +2

My sleep is moderately disturbed (2-3 hrs sleepless) +3

My sleep is greatly disturbed (3-5 hrs sleepless) +4

My sleep is completely disturbed (5-7 hrs sleepless) +5

10. Recreation

I am able to engage in all recreational activities with no neck pain at all +0

I am able to engage in all my recreational activities, with some pain in my neck +1

I am able to engage in most, but not all of my usual recreational activities because of pain in my neck +2

I am able to engage in a few of my usual recreational activities because of pain in my neck +3

I can hardly do any recreational activities because of pain in my neck +4

I can't do any recreational activities at all +5

11.3 Oswestry disability Index (ODI) (Fairbank & Pynsent, 2000)

Originally published in 1980 in *Physiotherapy*, the Oswestry Disability Index (ODI) is an outcome measure that was designed to assess function in activities of daily living for those with acute or chronic back pain.

The ODI consists of 10 patient-completed questions in which the response options are presented as 6-point Likert scales. Scores range from 0% (no disability) to 100% (most severe disability)

1. Pain Intensity

I have no pain at the moment +0

The pain is very mild at the moment +1

The pain is moderate at the moment +2

The pain is fairly severe at the moment +3

The pain is very severe at the moment +4

The pain is the worst imaginable at the moment +5

2. Personal Care (Washing, Dressing, etc.)

I can look after myself normally without causing extra pain +0

I can look after myself normally but it causes extra pain +1

It is painful to look after myself and I am slow and careful +2

I need some help but can manage most of my personal care +3

I need help every day in most aspects of self-care +4

I do not get dressed, I wash with difficulty and stay in bed +5

3. Lifting

I can lift heavy weights without extra pain +0

I can lift heavy weights, but it gives extra pain +1

Pain prevents me lifting heavy weights off the floor, but I can manage if they are conveniently placed, for example on a table +2

Pain prevents me from lifting heavy weights but I can manage light to medium weights if they are conveniently positioned +3

I can only lift very light weights +4

I cannot lift or carry anything at all +5

4. Walking

Pain does not prevent me walking any distance +0

Pain prevents me from walking more than 1 mile +1

Pain prevents me from walking more than ½ mile +2

Pain prevents me from walking more than 100 yards +3

I can only walk using a stick or crutches +4

I am in bed most of the time +5

5. Sitting

I can sit in any chair as long as I like +0

I can only sit in my favorite chair as long as I like +1

Pain prevents me sitting more than 1 hour +2

Pain prevents me from sitting more than 30 minutes +3

Pain prevents me from sitting more than 10 minutes +4

Pain prevents me from sitting at all +5

6. Standing

I can stand as long as I want without extra pain +0

I can stand as long as I want but it gives me extra pain +1

Pain prevents from standing for more than 1 hour +2

Pain prevents me from standing for more than 30 minutes +3

Pain prevents me from standing for more than 10 minutes +4

Pain prevents me from standing at all +5

7. Sleeping

My sleep is never disturbed by pain +0

My sleep is occasionally disturbed by pain +1

Because of pain I have less than 6 hours sleep +2

Because of pain I have less than 4 hours sleep +3

Because of pain I have less than 2 hours sleep +4

Pain prevents me from sleeping at all +5

8. Sex life (if applicable)

My sex life is normal and causes no extra pain +0

My sex life is normal but causes some extra pain +1

My sex life is nearly normal but is very painful +2

My sex life is severely restricted by pain +3

My sex life is nearly absent because of pain +4

Pain prevents any sex life at all +5

9. Social life

My social life is normal and gives me no extra pain +0

My social life is normal but increases the degree of pain +1

Pain has no significant effect on my social life apart from limiting my more energetic interests, for example sport +2

Pain has restricted my social life and I do not go out as often +3

Pain has restricted my social life to my home +4

I have no social life because of pain +5

10. Travelling

I can travel anywhere without pain +0

I can travel anywhere but it gives me extra pain +1

Pain is bad but I manage journeys over two hours +2

Pain restricts me to journeys of less than 1 hour +3

Pain restricts me to short necessary journeys under 30 minutes +4

Pain prevents me from travelling except to receive treatment +5

11.4 Modified Japanese Orthopedic Association (mJOA) score (Tetreault et al., 2017)

mJOA Scoring Criteria (18-point version)

Upper Extremity Motor Dysfunction (max score: 5)

0: I am unable to move my hands at all

1: I can move my hands a little, but I am unable to feed myself

2: I can feed myself but, I am unable to button my shirt

3: I can button up my shirt, but I find it very difficult and it takes a long time

4: I can button my shirt with only slight difficulty

5: My hands work normally

Lower Extremity Motor Dysfunction (max score: 7)

0: I am paralysed and unable to move or feel my legs

1: I can feel my legs but I am unable to move them at all

2: I can move my legs but I cannot walk

3: I can walk but I require a walking aid

4: Able I can walk up and down stairs, but I have to hold the handrail

5: I am a little unsteady on my feet, but I can walk up and down stairs without holding the handrail

6: I am a little unsteady, but I can walk unaided

7: My legs are unaffected

Sensory Dysfunction of Upper Extremity (max score: 3)

0: I am unable to feel my hands

1: I have pain or severe loss of feeling (including numbness, tingling) in my hands

2: I have mild loss of feeling (including numbness, tingling) in my hands

3: I have no loss of feeling in my hands

Sphincter function (max score: 3)

0: I cannot control when I pass urine

1: I have marked difficulty passing urine

2: I have mild difficulty passing urine

3: I have no difficulty passing urine

Score Interpretation

15-17: Mild myelopathy

12-14: Moderate myelopathy

0-11: Severe myelopathy

11.5 bladder, bowel, and sexual functionality

Sensation in the “saddle” area (buttocks, medial hips)

- Normal
- Paresthesia
- Reduced sensation
- Absent sensation

Bladder function:

- Normal function
- Mild dysfunction (occasional incontinence, but mostly continent)
- Moderate dysfunction (frequent incontinence, but some control)
- Severe dysfunction (total incontinence)

Bowel function - Low Anterior Resection Syndrome (LARS) Score (Bittorf et al., 2003):

1. Incontinence for Flatus:

- Never: 0 points
- Less than once per week: 4 points
- At least once per week: 7 points
- Daily: 10 points

2. Incontinence for Liquid Stool:

- Never: 0 points
- Less than once per week: 3 points
- At least once per week: 7 points
- Daily: 13 points

3. Frequency of Bowel Movements:

- 1 time per day or less: 0 points
- 2-3 times per day: 4 points
- 4-6 times per day: 7 points
- 7 or more times per day: 11 points

4. Clustering (Having multiple bowel movements in a short period):

- Never: 0 points
- Less than once per week: 9 points
- At least once per week: 11 points
- Daily: 13 points

5. Urgency (Sudden need to defecate):

- Never: 0 points
- Less than once per week: 11 points
- At least once per week: 16 points
- Daily: 18 points

Interpretation of Total Score:

- No LARS (0-20 points): Indicates normal or near-normal bowel function.
- Minor LARS (21-29 points): Indicates minor bowel dysfunction that may occasionally impact daily activities.
- Major LARS (30-42 points): Indicates significant bowel dysfunction with frequent symptoms that substantially impact daily life and quality of life.

Sexual functions

Male

- Normal erectile and ejaculatory function
- Mild erectile or ejaculatory dysfunction (able to have intercourse with mild difficulty)
- Moderate erectile or ejaculatory dysfunction (intercourse possible with significant difficulty or partial erection)
- Severe erectile or ejaculatory dysfunction (intercourse rarely or not possible)
- Complete loss of erectile and ejaculatory function

Female

- Normal sexual function
- Mild dysfunction (decreased arousal or lubrication, but able to have intercourse)
- Moderate dysfunction (significant difficulty with arousal or lubrication, painful intercourse)
- Severe dysfunction (intercourse rarely or not possible due to dysfunction)
- Complete loss of sexual function

11.6 Hospital Anxiety and Depression Scale (HADS) score (Stern, 2014):

Tick the box beside the reply that is closest to how you have been feeling in the past week.

Don't take too long over your replies: your immediate is best.

Don't take too long over your replies. Your immediate is best.

D	A	I feel tense or 'wound up':	D	A	I feel as if I am slowed down:
3		Most of the time	3		Nearly all the time
2		A lot of the time	2		Very often
1		From time to time, occasionally	1		Sometimes
0		Not at all	0		Not at all
		I still enjoy the things I used to enjoy:			I get a sort of frightened feeling like 'butterflies' in the stomach:
0		Definitely as much	0		Not at all
1		Not quite so much	1		Occasionally
2		Only a little	2		Quite Often
3		Hardly at all	3		Very Often
		I get a sort of frightened feeling as if something awful is about to happen:			I have lost interest in my appearance:
3		Very definitely and quite badly	3		Definitely
2		Yes, but not too badly	2		I don't take as much care as I should
1		A little, but it doesn't worry me	1		I may not take quite as much care
0		Not at all	0		I take just as much care as ever
		I can laugh and see the funny side of things:			I feel restless as I have to be on the move:
0		As much as I always could	3		Very much indeed
1		Not quite so much now	2		Quite a lot
2		Definitely not so much now	1		Not very much
3		Not at all	0		Not at all

	Worrying thoughts go through my mind:		I look forward with enjoyment to things:
3	A great deal of the time	0	As much as I ever did
2	A lot of the time	1	Rather less than I used to
1	From time to time, but not too often	2	Definitely less than I used to
0	Only occasionally	3	Hardly at all
	I feel cheerful:		I get sudden feelings of panic:
3	Not at all	3	Very often indeed
2	Not often	2	Quite often
1	Sometimes	1	Not very often
0	Most of the time	0	Not at all
	I can sit at ease and feel relaxed:		I can enjoy a good book or radio or TV program:
0	Definitely	0	Often
1	Usually	1	Sometimes
2	Not Often	2	Not often
3	Not at all	3	Very seldom

Please check you have answered all the questions

Scoring:

Total score: Depression (D) _____ Anxiety (A) _____

0-7 = Normal

8-10 = Borderline abnormal (borderline case)

11-21 = Abnormal (case)

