2.3 Aims

The goal of this study is to establish a multicenter cohort of patients operated on juxtamedullary tumors. With especial emphasis on functional outcome, quality indicators (QI) and quality of life after surgery three months after surgery. Causes of unfavorable outcome should be determined (Schipmann et al., 2017, 2019).

The main hypothesis is that early and less-invasive surgery with maximal extents of resection would lead to a more favorable outcome. In the future the registry would help assessing further hypothesis can be answered on the base of comparative effectiveness research (CER), examples of these hypothesis are:

1. Functional and neurological outcome in comparison to preoperative status. Comparison between Patients with good preoperative McCormick score (1-2) and those with a high preoperative score (3-5).
2. Risk-factors for non-favorable outcome
3. Non-Inferiority to achieve gross total resection via unilateral approaches
4. Question whether laminectomy as approach may cause more pain and impact quality of life
5. Risk factors for the development of CSF Leaks
6. Does bed rest prevent CSF leaks
7. Does laminectomy elevate the risk of CSF leaks
8. Does the utility of intraoperative neurophysiological monitoring (IOM) influence surgical outcome: rate of GTR and neurological outcome
9. Rate of postoperative kyphosis and deformity in laminectomy in comparison to non-laminectomy

10. Is facetectomy required for GTR of dumbbell tumors?

11. Risk factors for non-complete resection

Primary outcomes are determined by:

- Quality of life based on the questionnaire (EQ-D5)
- Extent of tumor resection (see CRF):
according to surgeon:
 1. Meningioma: Simpson grade 1 and 2
 2. Schwannoma: complete resection, including nerve root
 3. Cauda ependymoma: complete resection, including filum terminale
according to postoperative MRI, 3 months after surgery
 4. Other: surgeon's decision
- Neurological status (McCormick Score) (see CRF), 3 months after surgery

Secondary Outcome

Imaging: preoperative and postoperative MRI

- Volumetry
- Spinal canal occupancy ratio in %

Further patient reported outcomes:

- Functionality: Neck disability index (NDI) for tumors in the cervical spine, Oswestry disability index (ODI) for tumors in the thoracic and lumbar spine (see CRF)
- Local and radicular pain (VAS 1-10) (see CFR)
- Neurological status: motor function of each limb, ataxia and gait (mJOA score) (see CRF)
- HADS score- based score for anxiety

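### In the printed mJOA leg item, levels 5 and 6 are neither distinguishable nor in order, so an unchanged patient can score either

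*Protocol*

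**What the plan says.** Section 2.3 Aims lists the mJOA among the secondary outcomes, under further patient-reported outcomes, in the entry "Neurological status: motor function of each limb, ataxia and gait (mJOA score) (see CRF". The flow chart in section 1.2 schedules it at admission, 3 months and 12 months. Section 6.1 plans a comparison of neurological status and questionnaires before and after surgery.

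Section 11.4 prints the form in the first person. The leg item allows up to 7 points. Its third level is for patients who depend on a walking aid. The level above that concerns stairs and the rail: "4: Able I can walk up and down stairs, but I have to hold the handrail". One point higher, the rail is no longer needed and slight unsteadiness is added: "5: I am a little unsteady on my feet, but I can walk up and down stairs without holding the handrail". The level just below the maximum is then worded without any reference to stairs: "6: I am a little unsteady, but I can walk unaided". Level 7 is for unaffected legs. The section gives no instruction for the case in which more than one statement is true. It then bands the total as 0-11 severe, 12-14 moderate and 15-17 mild.

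**The concern.** A scored ordinal item needs levels that exclude each other and that improve as the points rise. Levels 5 and 6 do neither. The degree of unsteadiness is the same in both, and the level with more points asks for less, since it says nothing about stairs.

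The item is answered at up to three visits, and a pre/post comparison is planned. If a patient ticks 5 at one visit and 6 at the next, the record shows a change that did not happen. The information is lost when the answer is given. An analysis plan can merge levels afterwards, but it cannot recover which state the patient meant.

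**Working it through.** **Reproducing the plan's own figure.** The item maxima in section 11.4 are arm motor 5, leg motor 7, upper-limb sensation 3 and sphincter 3. The sum is 5 + 7 + 3 + 3 = 18, which agrees with the stated 18-point version. The leg item carries 7 of these points.

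**What each level demands, as printed.**

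| Level | Unsteadiness | Stairs | Walking aid |
|---|---|---|---|
| 4 | not mentioned | yes, handrail needed | not mentioned (level 3 covers needing one) |
| 5 | a little | yes, no handrail | not mentioned (level 3 covers needing one) |
| 6 | a little | not mentioned | none |

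**Overlaps.**

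- *5 and 6.* Anyone above level 3 is taken not to need a walking aid. A patient who meets level 5 is slightly unsteady and walks without an aid, so also meets level 6.
- *4 and 5.* These exclude each other: the handrail is either needed or not.
- *4 and 6.* These overlap only if a slightly unsteady patient who must hold the handrail on stairs still counts as walking without help. The text allows that reading but does not require it.

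**Would an unstated rule rescue the item?**

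- If the highest true level is taken, level 5 is practically never used, because whoever meets it also meets level 6.
- If the lowest true level is taken, slightly unsteady walkers who manage stairs without the rail go to 5, and those who need the rail go to 4. Level 6 is then left for slightly unsteady walkers who cannot manage stairs at all, and they outscore those who can.

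Either rule would make the scoring consistent. Neither puts 5 and 6 in a sensible order.

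**Size on the total.** Let S be the sum of the other three items (0 to 11). The total is S + leg level.

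- Choice between 5 and 6: (S + 6) - (S + 5) = 1 point.
- Choice between 4 and 6, on the wider reading: (S + 6) - (S + 4) = 2 points.

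**Size on the severity bands, should they be reported.** Each S from 0 to 11 was tried.

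| S | Leg 4 | Leg 5 | Leg 6 | Band differs, 5 or 6 | Band differs, 4 or 6 |
|---|---|---|---|---|---|
| 0-5 | 4-9 severe | 5-10 severe | 6-11 severe | no | no |
| 6 | 10 severe | 11 severe | 12 moderate | yes | yes |
| 7 | 11 severe | 12 moderate | 13 moderate | no | yes |
| 8 | 12 moderate | 13 moderate | 14 moderate | no | no |
| 9 | 13 moderate | 14 moderate | 15 mild | yes | yes |
| 10 | 14 moderate | 15 mild | 16 mild | no | yes |
| 11 | 15 mild | 16 mild | 17 mild | no | no |

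The other three items have 6 × 4 × 4 = 96 possible combinations. Those with S = 6, 7, 9 and 10 number 15, 13, 6 and 3. A choice between 5 and 6 changes the band in 15 + 6 = 21 of 96. A choice between 4 and 6 does so in 15 + 13 + 6 + 3 = 37 of 96. These are counts of score combinations, not shares of patients. The protocol gives no data on how often any combination occurs.

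**The case against.** The strongest defence reads the item as a ladder: walking aid, then handrail needed, then no handrail, then no help at all, then unaffected. On that reading a patient who has to hold a rail is not walking without help and belongs at level 4 only. This stands. It removes the overlap of 4 with 6 and the 2-point shift with it. It does not separate 5 from 6, because a patient who climbs stairs without the rail has already met the demand of level 6.

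The defence is also right about the limited reach of the problem. The mJOA is secondary, and the primary neurological measure is the McCormick score. The planned severity comparison also uses McCormick grades. No stated analysis uses the mJOA bands, and no regression names the mJOA as its outcome. A reader might infer that the fault runs through every model or regularly moves patients across a cut-off. The protocol supports neither: the band changes only at certain values of S, and a patient with no arm, sensory or sphincter deficit (S = 11) stays in the mild band at leg level 4, 5 or 6.

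A reader might also suspect disagreement between raters at different centres. The form is in the first person and listed as patient-reported, so the nearer mechanism is the patient's own choice, which can vary from visit to visit.

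Finally, it is tempting to say that the item was copied wrongly from the validated scale. The stray word in level 4 invites that thought, but the source scale is not among the documents and the attached CRF is not shown. The point rests on the printed wording alone.

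**Conclusion.** The fault holds on the printed text for levels 5 and 6: same unsteadiness, a smaller demand at the higher score, and no rule for choosing. The certain effect is 1 of 18 points without any change in the patient. An effect of 2 points needs the wider reading, in which using a handrail still counts as walking without help. It would be wrong to say that levels 4, 5 and 6 all overlap, because 4 and 5 exclude each other.

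What is at stake is avoidable measurement error, and possibly spurious change, in one secondary outcome compared before and after surgery. If the bands are tabulated, some patients may also be misclassified, but only at S = 6 or 9 for a 5/6 choice, or at S = 6, 7, 9 or 10 for a 4/6 choice. How many patients are affected cannot be estimated from the protocol. The conclusion assumes that the form in use carries the wording of the supplement, and that a patient at level 5 walks without an aid. It is worth correcting because data collection fixes the error, but it does not threaten the primary outcomes.

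**What to change.** 1. Check section 11.4 and the REDCap form against the mJOA version that the protocol intends to use. Correct the leg item so that levels 5 and 6 can be told apart and the higher score describes the better state.
2. If the intended version carries this same wording, keep it and print one selection rule that applies at all centres and visits.
3. Flag any records already collected on the printed wording. For these, add a sensitivity analysis that treats levels 5 and 6 as one level with a single value fixed in advance, and keep level 4 separate. Merging level 4 as well would throw away the valid distinction between 4 and 5. Leaving the merged level without a number would make the 18-point total impossible to compute.

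The cost is a correction to one supplement and one electronic form. The small downside is that flagged records lose the 5/6 distinction in the sensitivity analysis. The fixed value also matters for patients who enter or leave the merged level: a move from 4 into it counts as 1 point if the value is 5 and 2 points if it is 6. The value should therefore be stated before the data are analysed.

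### The mJOA is scored at every spinal level with one severity key from a cervical source, so with arms, hands and sphincter normal, even immobile but sensate legs are labelled moderate

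*Protocol*

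**What the plan says.** The Protocol lists the mJOA as a secondary outcome in the synopsis and in section 2.3 (Aims): "Neurological status: motor function of each limb, ataxia and gait (mJOA score". Neither place restricts it by spinal level. The same list does split the disability indices by level, with NDI for cervical tumours and ODI for thoracic and lumbar tumours. The flow chart (section 1.2) schedules the mJOA at admission, 3 months and 12 months, again with no restriction.

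Section 11.4 prints the instrument as "mJOA Scoring Criteria (18-point version". It has four domains: "Upper Extremity Motor Dysfunction (max score: 5", "Lower Extremity Motor Dysfunction (max score: 7", "Sensory Dysfunction of Upper Extremity (max score: 3", and sphincter function with a maximum of 3. The only interpretation key is "15-17: Mild myelopathy", "12-14: Moderate myelopathy" and 0 to 11 for severe. In the reference list, the source cited for section 11.4 is titled as setting these criteria in degenerative cervical myelopathy.

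Section 2.1 itself says that deficits depend on level: cervical tumours affect the upper extremities, and lumbar tumours affect the legs together with bladder, bowel and sexual function. The primary neurological outcome is the McCormick score (section 11.8), on which paraplegia is grade 5.

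**The concern.** A severity key built on a total with 8 arm and hand points assumes that those points can be lost. Where the tumour lies below the segments that serve the arms, they normally are not lost. The same label then stands for different degrees of disability in cervical and in lower tumours.

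Section 2.2 makes benchmarks of functionality and neurological outcome the purpose of the registry. If mJOA severity is tabulated with the printed key, isolated leg deficits in thoracic and lumbar patients would look milder than they are, and could disagree with the McCormick grade of the same patient. A mean or median absolute mJOA pooled over levels would also mix patients for whom 18 points can vary with patients for whom only 10 can.

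**Working it through.** **Inputs (section 11.4).** Maxima: arm motor 5, leg motor 7, hand sensation 3, sphincter 3. Bands: 0–11 severe, 12–14 moderate, 15–17 mild. Leg items: 0 = legs neither moved nor felt; 1 = "1: I can feel my legs but I am unable to move them at all"; 2 = legs move but the patient cannot walk; 3 = walks with an aid; 4 = stairs with the handrail; 7 = unaffected.

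**The plan's own figure.** 5 + 7 + 3 + 3 = 18, which matches the stated version.

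**Arms and hands unaffected.** Arm motor stays at 5 and hand sensation at 3, so

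total = 5 + 3 + leg + sphincter = 8 + leg + sphincter.

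- Minimum: 8 + 0 + 0 = 8. Maximum: 8 + 7 + 3 = 18.
- Constant share: 8/18 = 44%. Share that can vary: 10/18 = 56%.

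**Totals and bands** (S = severe, Mo = moderate, Mi = mild):

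| Leg score | Sphincter 0 | Sphincter 1 | Sphincter 2 | Sphincter 3 |
|---|---|---|---|---|
| 0 | 8 S | 9 S | 10 S | 11 S |
| 1 | 9 S | 10 S | 11 S | 12 Mo |
| 2 | 10 S | 11 S | 12 Mo | 13 Mo |
| 3 | 11 S | 12 Mo | 13 Mo | 14 Mo |
| 4 | 12 Mo | 13 Mo | 14 Mo | 15 Mi |
| 5 | 13 Mo | 14 Mo | 15 Mi | 16 Mi |
| 6 | 14 Mo | 15 Mi | 16 Mi | 17 Mi |
| 7 | 15 Mi | 16 Mi | 17 Mi | 18 (no band) |

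**Reading the last column (sphincter normal).** Leg scores 1, 2 and 3 give 12, 13 and 14, all moderate. A patient who needs the handrail scores 15, mild. On the McCormick scale, paraplegia is grade 5 and independence with an external aid is grade 3, so one mJOA band covers patients from McCormick 5 to McCormick 3.

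**How far the label problem reaches.** Immobile legs (leg 0 or 1) allow 2 × 4 = 8 combinations, of which 7 are severe and 1 is moderate. Non-walking (leg 0 to 2) allows 3 × 4 = 12 combinations, of which 9 are severe and 3 moderate. These are counts of score patterns, not of patients; the Protocol gives no figures from which patient frequencies could be derived.

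**Change from before to after surgery.** The constant cancels: (8 + leg₂ + sphincter₂) − (8 + leg₁ + sphincter₁) = (leg₂ − leg₁) + (sphincter₂ − sphincter₁). A patient with normal sphincter function who goes from leg 1 to leg 3 moves from 12 to 14. The total records +2, but the band does not change.

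**The case against.** The strongest case against the point has four parts.

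- **The mislabelled pattern is narrow.** A reader might infer that any thoracic or lumbar patient who cannot move the legs is graded moderate. The table does not support that: 7 of the 8 patterns with immobile legs are severe, and section 2.1 expects bladder and bowel disturbance with lumbar tumours. This stands. The point holds only for immobile legs with retained feeling and fully normal sphincter function, and for the neighbouring moderate cells.
- **The total still responds.** A reader might call it insensitive below the neck. It is not: 10 points vary with leg and sphincter function, and within-patient change, which is what section 6.1 plans to compare, is unaffected by the constant 8. This stands too.
- **No stated analysis uses the bands.** They appear only as an interpretation key in the supplement. The planned severity comparison uses McCormick 1–2 against 3–5, and McCormick is also the primary neurological outcome. This limits the consequence, and the documents do not support a claim that a planned band analysis is biased. It does not remove the point, because the key is the only interpretation rule the Protocol gives for this score and it is printed without a limit by level.
- **Leg and sphincter deficits are recorded elsewhere, and reporting by level could be left to an analysis plan.** The neurological examination, the ODI and the section 11.5 items do cover them, so no information is lost. But the unrestricted listing and the key are fixed in the Protocol itself, and that is where they can mislead.

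That a total of 18 has no band is not a material defect: it requires every item at its best value, and the bands name grades of myelopathy.

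**Conclusion.** The point holds in a limited form. With arms and hands unaffected, the mJOA total is confined to 8–18. With sphincter function also normal, the printed key gives one label, moderate, to patients from immobile but sensate legs (12) to walking with an aid (14), while McCormick grades paraplegia 5.

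What is affected is the severity label and any absolute mJOA value pooled across levels, both as secondary benchmarks. The change in total score, the primary neurological outcome and the planned McCormick comparison are not affected. This is a worthwhile low-cost improvement, not a threat to the registry's main results.

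The conclusion rests on two assumptions: that arm and hand function is normal in the thoracic and lumbar patients concerned, and that the printed key would be used if mJOA severity were reported. How many patients fall in the affected cells cannot be estimated from the Protocol.

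**What to change.** In section 11.4 and in the outcome lists (synopsis and section 2.3, Aims), state that the mild, moderate and severe bands are used for cervical tumours only. For thoracic and lumbar tumours, report the lower-extremity and sphincter subscores beside the total, by level and without bands.

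The subscores are already collected, so the change needs no new data and no extra visit. The cost is level-specific tables and the loss of a single severity distribution pooled over the whole registry.
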